### Analysis Timepoints

Unless otherwise specified, the baseline value will be defined as the last non-missing evaluation prior to the first dose of study medication.

### Methods for Handling Missing Data

No imputation of values for missing data will be performed. All data recorded on the case report form will be included in the listings that will accompany the clinical study report. Missing pharmacodynamic data, including reasons for the missing data, will be listed by subject and examined on a case-by-case basis to determine if these affect subject allocation.

## 7. STUDY SUBJECTS

---

Unless otherwise specified, summary tables for disposition, major protocol deviations, and demographics and other baseline characteristics will be presented for the Safety Population.

### Disposition

Subject disposition will be summarized for all subjects enrolled in this study and for each analysis population, including:

- The number of subjects enrolled;
- The number of subjects randomized;
- The number and percentage of subjects who received study product at each study day;
- The number and percentage of subjects who completed each study part;
- The number and percentage of subjects discontinued from the study by primary reason for discontinuation;
- The number and percentage of subjects included in each of the study populations.

The percentages will be calculated using the number of subjects randomized as denominator.

A listing of subject's disposition will be provided. A listing of subjects included in each of the analysis populations will also be provided.

A listing presenting the subject ID and the corresponding randomization numbers will be provided as well.

### Protocol Deviations

A listing of all protocol deviations will be provided. A separate listing will be generated for blood sampling time deviations.

The time of blood sample collection will be calculated according to the product administration schedule. For postdose samples, all deviations from the scheduled sampling time of more than 1 minute for the first 30 minutes and more than 5 minutes for the remaining samples will be reported in the final report. Actual elapsed time from dose administration will be used for evaluation of plasma PK parameters.

Subjects with inclusion/exclusion criteria violation will be presented in a separate listing.

## 8. DEMOGRAPHIC AND OTHER BASELINE CHARACTERISTICS

---

### Demographic and Baseline Characteristics

Demographic data and baseline characteristics will be presented in a data listing and summarized in a table by study population. Quantitative assessments to be summarized are age, height, body weight at screening and body mass index (BMI). Subject demographics include sex, age, ethnicity, and race. Age will be calculated from the date of birth to the date that the informed consent form was signed if it is not collected on the CRF. In addition, number of tobacco product used per day as well as the duration of tobacco use (derived as the interval between tobacco use start date and end date) will be summarized by type of tobacco use as well. Responses for smoking history and number of tobacco products used per day will be listed by type of tobacco use in the substance usage listing.

### Medical History

Any medical history findings will be recorded and presented in a listing. The listing will include the MedDRA 21.0 coding terms (e.g., SOC and preferred terms).

### Medication History

All medications, including prescription, over-the-counter, or herbal therapies used by the subjects will be documented for the 30 days prior to Screening will be recorded and presented as prior medication in a listing. The listing will include the WHO DDE (March 1, 2018) coding terms (e.g., ATC and Preferred Term).

### Childbearing Potential and Contraceptive Method

Childbearing potential and, if applicable, contraceptive method will be recorded and presented in a listing for all female subjects.

## 9. PHARMACOKINETIC AND PHARMACODYNAMIC ANALYSES

### Pharmacodynamic

#### VAS Scores

Responses to Tobacco/Nicotine Withdrawal and Direct Effects of the Product Questionnaires recorded as VAS scores will be treated as continuous variables. Data listings of VAS scores for each questionnaire item will be provided for each subject.

For the Tobacco/Nicotine Withdrawal questionnaire, the reduction in VAS score will be calculated using the difference between pre-use and post-use values at each time point for each treatment (i.e.  $VAS_{pre-use1} - VAS_{post-use1}$ ).

Responses to each Tobacco/Nicotine Withdrawal Questionnaire and Direct Effects of Product Questionnaire item, as well as the Tobacco/Nicotine Withdrawal reduction from pre-use, will be summarized by time point for each study product, and product use condition using the following descriptive statistics (n, mean, SD, median, Q1, Q3, minimum, maximum, CV%). Individual and mean figures for the responses to Tobacco/Nicotine Withdrawal Questionnaire (unadjusted and baseline adjusted) and Direct Effects of Product Questionnaire item will be presented using linear scale.

#### PD Parameters

The following subjective effect parameters will be calculated for each subject and treatment:

Questionnaire	PD Parameter	Definition
Tobacco/Nicotine Withdrawal Questionnaire	$E_{max\_item(controlled)}$	The maximum reduction in VAS score for each item during the first product use in Part B
	$E_{max\_item(uncontrolled)}$	The maximum reduction in VAS score for each item during the second product use in Part B
Direct Effects of Product Questionnaire	$E_{max\_item(controlled)}$	The largest VAS score recorded for the response to each item during the first product use in Part B
	$E_{max\_item(uncontrolled)}$	The largest VAS score recorded for the response to each item during the second product use in Part B

The definition of the different item in each questionnaire is detailed in the table below.

Questionnaire	Item	Question
Tobacco/Nicotine Withdrawal Questionnaire	$E_{max\_urge(controlled)}$ $E_{max\_urge(uncontrolled)}$	Urge to smoke
	$E_{max\_anx(controlled)}$ $E_{max\_anx(uncontrolled)}$	Anxious
	$E_{max\_diffct(controlled)}$ $E_{max\_diffct(uncontrolled)}$	Difficulty Concentrating
	$E_{max\_impat(controlled)}$ $E_{max\_impat(uncontrolled)}$	Impatient
	$E_{max\_crav(controlled)}$ $E_{max\_crav(uncontrolled)}$	Craving a Cigarette

Direct Effect of Product	$E_{max\_plst}(\text{controlled})$	Is the product "Pleasant" right now?
	$E_{max\_plst}(\text{uncontrolled})$	
	$E_{max\_stf}(\text{controlled})$	Is the product "Satisfying" right now?
	$E_{max\_stf}(\text{uncontrolled})$	
	$E_{max\_calm}(\text{controlled})$	Is the product making you feel "Calm" right now?
	$E_{max\_calm}(\text{uncontrolled})$	
	$E_{max\_conc}(\text{controlled})$	Is the product helping you "Concentrate" right now?
	$E_{max\_conc}(\text{uncontrolled})$	
	$E_{max\_awake}(\text{controlled})$	Is the product making you feel more "Awake" right now?
	$E_{max\_awake}(\text{uncontrolled})$	
	$E_{max\_sick}(\text{controlled})$	Is the product making you feel "Sick" right now?
	$E_{max\_sick}(\text{uncontrolled})$	
	$E_{max\_hunger}(\text{controlled})$	Is the product reducing your "Hunger" for food right now?
	$E_{max\_hunger}(\text{uncontrolled})$	
	$E_{max\_more}(\text{controlled})$	Would you like "More" of the product right now?
	$E_{max\_more}(\text{uncontrolled})$	

The items  $E_{max\_urge}(\text{controlled})$  and  $E_{max\_plst}(\text{controlled})$  will be the primary endpoints of the study while the remaining items will be secondary endpoints.

## Statistical Analysis of Subjective Effect Parameters

A linear mixed effects model for analysis of variance/covariance (Proc Mixed) will be performed on  $E_{max\_urge}(\text{controlled})$  and  $E_{max\_plst}(\text{controlled})$ . The model will include  $E_{max}$  as the response variable, sequence, study product, and period as fixed model effects, baseline score as a covariate, and subject nested-within sequence as a random effect. Sequence will be tested using subject nested-within-sequence as the error term. Least square mean (LSM) and 95% confidence interval (CI) for each study product group will be provided. Comparisons will be made for Product A vs. B, A vs. C and B vs. C. The comparison between Product A and Product C will be used as a comparison for internal validity. The LSM difference, p-value and 95% CI of the difference will be provided.

The SAS code for the statistical modeling is:

```
Proc MIXED data=test;
  class subject sequence period product;
  model Emax = sequence period product baseline / ddfm=KR;
  random subject (sequence) / type=UN;
  estimate "Product A vs Product B" product 1 0 -1 /cl alpha=0.05;
  estimate "Product A vs Product C" product 1 0 -1 /cl alpha=0.05;
  estimate "Product B vs Product C" product 0 1 -1 /cl alpha=0.05;
  lsmeans product/cl alpha=0.05;
run;
```

The same model will be used for  $E_{max\_urge}(\text{uncontrolled})$  and  $E_{max\_plst}(\text{uncontrolled})$ , and all  $E_{max}$  of other questions in the Tobacco/Nicotine Withdrawal Questionnaire and Direct Effects of Product Questionnaire for the controlled and uncontrolled product uses in Part B. Baseline (pre-use) score will be included as a covariate for all pharmacodynamics measures for which a pre-use score is collected.

The analysis on  $E_{max\_urge(\text{controlled})}$  and  $E_{max\_plist(\text{controlled})}$  will be based on the pharmacodynamic and the completer populations separately.

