9.6. Blinding

The study design is not blinded since subjects will know if the product is a VLN cigarette, their own cigarette or a nicotine polacrilex gum. The study product codes will be open to all study staff and to the Sponsor. The randomization code will not be available to the personnel of the bioanalytical facility until the bioanalytical tables have been finalized and audited by the Quality Assurance (QA) department.

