12.4.3.2. Part B

Responses to each Tobacco/Nicotine Withdrawal Questionnaire and Direct Effects of Product Questionnaire item will be summarized by time point for each study product, and product use condition. For Tobacco/Nicotine Withdrawal VAS scores, descriptive statistics (n, mean, SD, median, Q1, Q3, min, max) for the difference from pre-use at each time point will also be reported. Derived parameters (E_{max}) for each questionnaire item will be summarized using descriptive statistics.

A linear mixed effects model for analysis of variance/covariance (Proc Mixed) will be performed on $E_{max_urge(controlled)}$ and $E_{max_plst(controlled)}$. The model will include E_{max} as the response variable, sequence, study product, and period as fixed model effects, baseline score as a covariate (for E_{max_urge} only), and subject nested-within sequence as a random effect. Sequence will be tested using subject nested-within-sequence as the error term. Least square mean (LSM) and 95% confidence interval (CI) for each Study Product group will be provided. Comparisons will be made for Product A vs. B, A vs. C and B vs. C. The comparison between Product A and Product C will be used as a comparison for internal validity. The LSM difference, p-value and 95% CI of the difference will be provided.

The same model will be used for $E_{max_urge(uncontrolled)}$ and $E_{max_plst(uncontrolled)}$, and all E_{max} of other questions in the Tobacco/Nicotine Withdrawal Questionnaire and Direct Effects of Product Questionnaire for the controlled and uncontrolled product uses in Part B. Responses to Use the Product Again VAS will be summarized by study product using descriptive statistics (n, mean, SD, median, Q1, Q3, min, max). A summary table of frequencies may also be provided.

Descriptive statistics (n, mean, SD, median, Q1, Q3, min, max) will be provided on duration of time a product is used (time spent per cigarette and duration of gum in mouth), number of inhalations (puffs), and duration of inhalation (per puff) per cigarette for own-brand and VLN cigarettes.

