12.4.3.3. Adjustment for Covariates

Baseline (pre-use) score will be included as a covariate for all pharmacodynamics measures for which a pre-use score is collected.

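### The primary pharmacodynamic model pools between- and within-subject baseline slopes; product contrasts may be biased if mean pre-use scores differ by product and the two slopes also differ

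*SAP*

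**What the plan says.** SAP section 9 (Statistical Analysis of Subjective Effect Parameters) gives the code for both primary endpoints, E_max_urge(controlled) and E_max_plst(controlled), and applies the same model to the other Part B questionnaire items. The fixed part is "model Emax = sequence period product baseline / ddfm=KR" and the subject term is "random subject (sequence) / type=UN". No subject-mean baseline, fixed-subject model or other sensitivity model separates the two slopes; the completer analysis changes only the population.

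The documents do not agree on what the covariate is:

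- SAP section 9, VAS Scores, builds the urge response from each session's own pre-use score: "the reduction in VAS score will be calculated using the difference between pre-use and post-use values at each time point for each treatment".
- SAP section 6, Analysis Timepoints, has a general rule: "Unless otherwise specified, the baseline value will be defined as the last non-missing evaluation prior to the first dose of study medication".
- Protocol 12.4.3.2 has "baseline score as a covariate (for E_{max_urge} only), and subject nested-within sequence as a random effect".
- Protocol 12.4.3.3 says "Baseline (pre-use) score will be included as a covariate for all pharmacodynamics measures for which a pre-use score is collected". The schedule of assessments gives the Direct Effects questionnaire a pre-use time point, so this would include Pleasant.
- SAP section 12 reports no changes from the protocol.

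**The concern.** Each subject contributes three pre-use scores in the Part B controlled sessions. With a random intercept, the model estimates the covariate slope partly from differences between subjects and partly from differences between a subject's own days. The contrasts A-B, A-C and B-C rest on within-subject comparisons. If the pooled slope differs from the within-subject slope, the adjustment removes too much or too little of any difference in mean pre-use score between products.

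The slopes have reason to differ for urge. The response contains the pre-use score, so day-to-day variation in that score enters E_max_urge with a slope near 1. A subject who habitually rates high does so before and after use, which lowers the between-subject slope.

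Mean pre-use scores could also differ by product. Protocol 9.6 states "The study design is not blinded since subjects will know if the product is a VLN cigarette", and every subject has used all three products in Part A. The sequences ABC, BCA and CAB give each product one fixed predecessor in periods 2 and 3: A follows C, B follows A, C follows B. At stake are the point estimate and confidence interval coverage of the primary contrasts.

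**Working it through.** **Planned figure.** Protocol 12.2 and SAP section 4 assume an own-brand versus gum difference of 15.85 with SD 28.44, two-sided alpha 0.05, and 54 completers for more than 80% power. Taking 28.44 as the per-period SD, the SD of a paired difference is √2 × 28.44 = 40.22. A paired t test then needs 53 subjects and has power 0.811 at 54, so the figure is reproduced. It uses no covariate, and this point does not change it.

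**Formula.** For a random-intercept model with one slope:

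- fitted slope = (1 − w) × b_within + w × b_between
- error in a product contrast = w × (b_within − b_between) × (difference in mean pre-use score)

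The weight w comes from the information at each level. With 54 subjects in 3 sequences there are 51 between-subject degrees of freedom. There are 108 − 4 = 104 within-subject degrees of freedom after product and period. With ICCx the intraclass correlation of the pre-use score and ICCy that of E_max:

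- between = 51 × (1 + 2·ICCx)/(1 + 2·ICCy)
- within = 104 × (1 − ICCx)/(1 − ICCy)
- w = between/(between + within)

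At ICCx = ICCy = 0.5: 51/(51 + 104) = 0.329. The documents give neither correlation, so a range is shown:

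| ICCx | ICCy 0.2 | ICCy 0.5 | ICCy 0.7 |
|---|---|---|---|
| 0.3 | 0.390 | 0.219 | 0.123 |
| 0.5 | 0.528 | 0.329 | 0.197 |
| 0.7 | 0.692 | 0.495 | 0.329 |

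For an assumed 10-point difference in mean pre-use score:

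- smallest: 0.123 × 0.2 × 10 = 0.25 points
- middle: 0.329 × 0.4 × 10 = 1.32 points
- largest: 0.692 × 0.6 × 10 = 4.15 points

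**Simulation check.** The SAP model and a model splitting the pre-use score into subject mean and deviation were fitted by REML (54 subjects, ABC/BCA/CAB, 1500 runs per case). Assumptions: residual SD 28.44, pre-use SD 18 between and 18 within subjects, subject SD 20, own-brand pre-use mean raised by the stated amount. Bias is in B-C, with Monte Carlo SE about 0.15. The between slope shown is on the subject's underlying level; on the observed mean of three scores it lies closer to the within slope.

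| Slopes within/between | Pre-use difference | Bias, coverage: SAP | Bias, coverage: split | SE SAP/split |
|---|---|---|---|---|
| 0.6/0.2 | 0 | +0.13, 95.5% | +0.13, 95.1% | 5.50/5.49 |
| 0.4/0.4 | 10 | +0.11, 95.1% | +0.06, 95.2% | 5.60/5.71 |
| 0.6/0.2 | 5 | +0.76, 95.1% | +0.10, 95.1% | 5.53/5.55 |
| 0.6/0.2 | 10 | +1.39, 94.7% | +0.06, 95.2% | 5.62/5.71 |
| 0.6/0.2 | 10, periods 2-3 only | +0.96, 94.9% | +0.08, 95.1% | 5.55/5.59 |
| 0.8/0.2 | 10 | +2.00, 94.0% | +0.06, 95.2% | 5.65/5.71 |
| 0.8/0.2, pre-use SD 22/12, subject SD 14 | 10 | +4.20, 88.5% | +0.03, 95.0% | 5.68/5.96 |

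The fitted SAP slopes agree with the formula: 0.473 in the fourth row gives (0.6 − 0.473) × 10 = 1.27, and 0.391 in the last row gives (0.8 − 0.391) × 10 = 4.09.

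Rows 1 and 2 show that both conditions are needed. In row 1, chance differences in pre-use means had SD 3.36 and moved the estimate by 0.127 points per point. A one-SD imbalance therefore costs 3.36 × 0.127 = 0.43 points in a given trial and averages to zero.

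**Pleasant, if the covariate is kept.** With assumed slopes of 0.3 to 0.4 within and 0.8 between, simulated absolute bias was 1.5 to 3.0 points at a 10-point pre-use difference (coverage 90-93%) and 3.1 to 6.3 at 20 points (coverage 79-90%).

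**The case against.** A reader might infer that the contrasts are biased whenever mean pre-use scores differ by product. The documents do not support that, because the slopes must differ too. A reader might also infer that the error shrinks the VLN versus own-brand difference. Its sign depends on which product has the higher pre-use mean and which slope is larger; in the runs above it enlarges own-brand's advantage over gum. Nor does any document show a systematic pre-use difference. About 20 hours of abstinence before each controlled session limits carryover, though it does not exclude it.

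On a literal reading of the SAP's general baseline rule there is one value per subject, and the problem cannot arise. That rule yields where something else is specified. Section 9 specifies the pre-use score, and the questionnaires are scheduled only in Part B apart from Day -1 training. The session-specific reading is the workable one, but the SAP should say so.

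The Pleasant figures depend on a covariate that Protocol 12.4.3.2 confines to urge. If that section governs, they fall away.

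The strongest objection is that the within-subject slope may itself be inflated by rating noise. Suppose day-to-day state has SD 8 and slope 0.4, and noise has SD 12 and slope 1. The within slope on the observed score is (0.4 × 64 + 144)/208 = 0.815. For a true 10-point shift in pre-use urge, the split model over-adjusts by (0.815 − 0.4) × 10 = 4.2 points; the SAP model simulated under the same assumptions (subject slope 0.4) over-adjusts by 2.6. This stands as a real drawback of the split. It does not defend pooling: both models miss a target (equal true urge) that the SAP does not set, since it adjusts on the observed score.

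**Conclusion.** The concern holds in conditional form. As coded, and with the session-specific covariate, the model mixes two slopes and may bias the product contrasts if mean pre-use scores differ by product and the slopes differ. For urge, an assumed 10-point pre-use difference and a slope gap of 0.2 to 0.6 give an error of roughly 0.3 to 4 VAS points in either direction, or 0.25/15.85 = 2% to 4.15/15.85 = 26% of the planned own-brand versus gum difference. In the urge runs tabulated, coverage falls clearly below 95% only when a large slope gap meets a 10-point difference. Every slope, variance split and pre-use difference here is an assumption. The finding justifies a change to the SAP; it does not show that the trial's result would be wrong.

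**What to change.** In SAP section 9, define baseline as the pre-use score of the same session. Reconcile this with the general rule in SAP section 6 and with Protocol 12.4.3.2 and 12.4.3.3, stating whether Pleasant has a covariate. Record the outcome in SAP section 12.

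For E_max_urge(controlled), and for every controlled-session item that keeps the covariate, derive BASEMEAN (the subject's mean pre-use score over the Part B controlled sessions) and BASEDEV (the session score minus BASEMEAN). Fit `model Emax = sequence period product basedev basemean / ddfm=KR`, with least squares means at BASEDEV = 0 and the average BASEMEAN. Adding BASEMEAN beside the existing baseline term gives the same product contrasts. Report the single-slope model as supportive.

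The cost is two derived variables and one degree of freedom, with no new data. Precision is unchanged when pre-use means are equal. At a 10-point difference the SE rises by about 0.1 to 0.3 in the runs above. With equal slopes, where the split is not needed, power for the planned effect goes from 0.801 to 0.787. The SAP should also disclose that the split over-adjusts more than the single slope if the pre-use score is mostly rating noise.

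A separate error in the same code block should be corrected at the same time: the A versus B estimate carries the A versus C coefficients (1 0 −1).

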12.2. Determination of Sample Size

Sample size estimation was performed on both pharmacodynamic endpoints.

Using a 2-sided Type I error rate at $\alpha=0.05$ and assuming a mean difference in $E_{max_urge(\text{controlled})}$ between own-brand cigarette and nicotine polacrilex gum of 15.85 points and standard deviation (SD) of 28.44, 54 completed subjects will be required to detect a significant difference between own-brand cigarette and nicotine polacrilex gum with greater than 80% power.

Using a 2-sided Type I error rate at $\alpha=0.05$ and assuming a mean difference in $E_{max_plst(\text{controlled})}$ between own-brand cigarette and nicotine polacrilex gum of 35.21 points and SD of 31.82, estimate based on data obtained from the study site, 16 completed subjects will be adequate to detect a significant difference between own-brand cigarette and nicotine polacrilex gum with greater than 80% power.

An appropriate number of subjects will be randomized on Day 1 (Part A) to ensure that a minimum of 54 subjects complete the study. Replacement subjects may be enrolled to ensure that the minimum number of subjects complete the study.

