Part B will begin upon completion of Part A. Subjects will be randomized to one of three product sequence groups in Part B, which will consist of 3 study days (Days 4 to 6), with one product per day. Each study day will consist of: 1) Controlled Product Use Session (10 puffs from their own-brand cigarette or VLN cigarette [maximum  $3 \pm 2$  seconds per puff] at approximately  $30 \pm 5$ -second interpuff intervals, or chew the nicotine polacrilex gum using the "chew and park" method for 10 minutes); and 2) Uncontrolled Product Use Session (use of one unit of a product ad libitum for 10 minutes). The Controlled Product Use Session and Uncontrolled Product Use Session will be separated by approximately 6 hours. During Part B, pharmacodynamic measures, PK samples, and product use behavior (Uncontrolled Product Use Session only) will be collected at various time points each day.

Safety assessments, including AEs, physical examinations, vital signs (respiratory rate, pulse rate, blood pressure, and oral temperature), electrocardiogram (ECG), clinical laboratory tests (clinical chemistry, hematology, urinalysis, and serology), urine drug screen, and alcohol test will be collected at designated time points throughout the study.

Subjects will be discharged from the clinic on Day 6 once all procedures are completed (or at Early Termination).

Figure 1: Overview of Study Design

† Ad libitum use of the nicotine gum for 10 minutes. Subjects will be instructed on how to correctly use the nicotine gum using the “chew and park” method.

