### Sample Size Determination

Sample size estimation was performed on both pharmacodynamic endpoints.

Using a 2-sided Type I error rate at  $\alpha=0.05$  and assuming a mean difference in  $E_{max\_urge(\text{controlled})}$  between own-brand cigarette and nicotine polacrilex gum of 15.85 points and standard deviation (SD) of 28.44, 54 completed subjects will be required to detect a significant difference between own-brand cigarette and nicotine polacrilex gum with greater than 80% power. Using a 2-sided Type I error rate at  $\alpha=0.05$  and assuming a mean difference in  $E_{max\_plst(\text{controlled})}$  between own-brand cigarette and nicotine polacrilex gum of 35.21 points and SD of 31.82, estimate based on data obtained from the study site, 16 completed subjects will be adequate to detect a significant difference between own-brand cigarette and nicotine polacrilex gum with greater than 80% power.

An appropriate number of subjects will be randomized on Day 1 (Part A) to ensure that a minimum of 54 subjects complete the study. Replacement subjects may be enrolled to ensure that the minimum number of subjects complete the study.

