#### Statistical Analysis of PK Parameters

A linear mixed model for analysis of variance (Proc Mixed) will be performed on the baseline-adjusted log transformed nicotine PK parameters in Part B ( $C_{\text{max}}(\text{controlled})$ ,  $C_{\text{max}}(\text{uncontrolled})$ ,  $AUC_{(\text{controlled})}$  and  $AUC_{(\text{controlled})}$ ). The model will include sequence, study product, and period as fixed effects and subject nested-within sequence as a random effect. Sequence will be tested using subject nested-within sequence as the error term. From each model, the geometric LSM and 95% confidence intervals will be calculated for each study product. Separate analyses will be performed on the parameters calculated for the Controlled and Uncontrolled Use sessions. Geometric mean ratios for each pair comparison, 95% confidence interval and p value will be provided.

The SAS codes for the model will be as follows:

```
Proc MIXED data=test;
  class subject sequence period product;
  model log(Cmax0_180) = sequence period product / ddfm=KR;
  random subject (sequence) / type=UN;
  estimate "Product A vs Product B" product 1 -1 0 /cl alpha=0.05;
  estimate "Product A vs Product C" product 1 0 -1 /cl alpha=0.05;
  estimate "Product B vs Product C" product 0 1 -1 /cl alpha=0.05;
  lsmeans product/cl alpha=0.05;
run;
```

The Hodges-Lehmann's method will be used to estimate the median differences and the 95% confidence interval of  $T_{\text{max}}$  and  $T_{1/2}$  between the products for controlled and uncontrolled use.

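### The printed PROC MIXED code for the PD and PK models requests an unstructured covariance across all subjects, not the single random subject effect that the text specifies

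*SAP*

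**What the plan says.** SAP section 9, *Statistical Analysis of Subjective Effect Parameters*, describes the PD model in words, with "baseline score as a covariate, and subject nested-within sequence as a random effect". The code that follows declares "class subject sequence period product", then "model Emax = sequence period product baseline / ddfm=KR", then "random subject (sequence) / type=UN". No SUBJECT= option appears.

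The SAP section 9 text on *Statistical Analysis of PK Parameters* has "study product, and period as fixed effects and subject nested-within sequence as a random effect", and its code repeats the same RANDOM statement. Protocol sections 12.4.3.2 and 12.4.4 describe the same single random effect. So do the footnotes to the PD and PK table shells in SAP Appendix C. None of these places mentions an unstructured covariance matrix.

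On size, the SAP plans recruitment "to ensure that a minimum of 54 subjects complete the study", and describes Part B as a part "which will consist of 3 study days (Days 4 to 6), with one product per day". Each completer therefore gives three values of any one Emax.

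**The concern.** In PROC MIXED, SUBJECT= divides the random-effects covariance matrix G into independent, identical blocks, and TYPE= sets the structure inside a block. Without SUBJECT=, the data form one block. Since subject is a CLASS variable, the random term has one level per subject. An unstructured type then asks for a separate variance for every subject and a covariance for every pair of subjects, from a single realisation of the subject effects.

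That is not the stated model, and it is not a minor variant. The PD code serves 13 questionnaire items in two sessions (13 × 2 = 26 Emax analyses), including both primary endpoints, which are repeated in the Completer Population. The PK code serves Cmax and AUC in both sessions. If the code fails, the printed specification yields no result. If it stops at a degenerate solution that someone accepts, the confidence intervals for the product differences are too narrow.

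**Working it through.** **Inputs.** 54 completers (SAP section 4, Sample Size Determination); 3 periods (SAP section 3); sequences ABC, BCA, CAB; fixed effects and RANDOM statement as printed in SAP section 9. The meaning of TYPE= and SUBJECT= is standard PROC MIXED behaviour. It is taken as given, because SAS was not available.

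**The plan's own figure.** The 54 sets the dimension of G and is not disputed. Reading the stated SD of 28.44 as within-subject, the noncentrality is 15.85 / (28.44 × √(2/54)) = 2.90. With 52 degrees of freedom and two-sided α = 0.05, power is 0.811, which agrees with the stated figure of more than 80%.

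**Parameter count.**
- Values: 54 × 3 = 162.
- Printed code: 54 × 55 / 2 = 1,485 in G, plus 1 residual = 1,486.
- Stated model: 1 subject variance + 1 residual = 2.

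**Identifiability.** Let Z be the subject design matrix and P the REML projection after the fixed effects. Sequence removes 3 between-subject directions, so Z′PZ has rank 54 − 3 = 51 (confirmed numerically, with and without the baseline covariate). At most 51 × 52 / 2 = 1,326 directions of G carry REML information, and 1,485 − 1,326 = 159 are unidentified whatever the data. As a check on simulated data, adding c to every element of G linking subjects of one sequence left −2 REML log-likelihood at 1195.116581 for c = 0, 100 and 10,000.

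**What a degenerate fit would do.** One simulated 54 × 3 data set for each form of the model, with assumed between-subject SD 18 and residual SD 20. The intended model is compared with a rank-one G (all subject effects perfectly correlated), which the unstructured type permits:

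| | Intended | Rank-one G |
|---|---|---|
| With baseline: −2 REML log-likelihood | 1195.12 | 1076.02 |
| Residual variance | 446.6 | 302.3 |
| B − A estimate | 16.904 | 16.913 |
| SE of B − A | 4.068 | 3.347 |
| No covariate: −2 REML log-likelihood | 1138.59 | 1042.51 |
| Residual variance | 372.2 | 251.4 |
| B − A estimate | 20.167 | 20.167 |
| SE of B − A | 3.713 | 3.051 |

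SE ratios: 3.347 / 4.068 = 0.823 and 3.051 / 3.713 = 0.822.

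The mechanism is simple. Without a covariate and with complete data, the intended residual has 162 − 54 − 2 (period) − 2 (product) = 104 degrees of freedom. A rank-one G absorbs the between-subject variation with one parameter, so the same within-subject sum of squares is divided by 162 − 7 (fixed effects) − 1 = 154. The variance ratio is 104 / 154 = 0.675, and √0.675 = 0.822, as simulated. This explains why the ratio hardly depends on the assumed SDs. Over four between/within SD pairs (10/25, 18/20, 25/15, 20/28.44) with 8 data sets each, it stayed at 0.82 to 0.83, and the rank-one G had the lower −2 REML log-likelihood in all 32.

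**Effect on a test.** With SEs multiplied by 0.82, the 1.96 threshold acts as 1.96 × 0.82 = 1.61. By the normal approximation, a nominal two-sided 5% test then runs near 11%.

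**The case against.** The strongest reply is that the model is already fixed in words, in the SAP text, the protocol and the table footnotes, and that code this over-parameterised would not pass unnoticed. With 1,486 covariance parameters, 162 values and Kenward-Roger degrees of freedom, one expects non-convergence, a singular Hessian or a resource error. SAP section 13 also requires all analysis programs to be validated. This largely stands, and it limits the consequence. It does not make the printed code correct.

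A reader might infer that, once the code fails, someone must choose a new covariance structure after seeing open-label data. The documents do not support that: the stated random effect leaves one correction, which is to drop the option.

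A reader might also infer that the fit is certain to crash, or certain to land on a degenerate matrix. Neither is shown. A better likelihood at a rank-one G does not say where PROC MIXED stops or what it prints.

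Finally, one could say that the unstructured type is harmless for a scalar effect. That would hold for a random intercept with SUBJECT= given, where the block is 1 × 1. The printed statement has no SUBJECT=. Even on that reading the option does nothing and should go.

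**Conclusion.** Wrong as written, and a simple code correction. The RANDOM statement in both blocks does not fit the model that the SAP and protocol describe: 1,485 covariance parameters plus a residual, against 2. The count and the 159 unidentified directions rest only on 54 completers, three periods, the fixed effects and standard PROC MIXED syntax; a larger analysis population makes the count larger.

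The likely outcome is a visible failure, but this was not observed. The loss of about 18% in the contrast standard errors applies only if a rank-one fit were accepted, and it comes from simulated data with assumed variances. Product-contrast estimates were unchanged without a covariate and differed by about 0.01 point with one (16.904 against 16.913), so the exposure is to interval width and p-values, not to the size of the estimated differences. The sample size is unaffected.

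**What to change.** In both SAP section 9 code blocks, delete `/ type=UN`, which leaves `random subject(sequence);`, or write `random intercept / subject=subject(sequence);`. Either fits the one-variance random subject effect in the text. Run both blocks on dummy data before database lock and confirm that the output reports two covariance parameters and that the model converges.

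The cost is one line in two places and a short test run, with no change to design, data collection or power. The test run has a further use: in the PD block the A vs B ESTIMATE carries the same coefficients (1 0 -1) as A vs C. That is a separate error, which would run without warning.
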